9.3 Exclusion Criteria

1. Diabetes of any type
2. Taking metformin or any other glucose lowering medication
3. Other diabetes medication
4. Active malignancy of any kind
5. Clinically relevant renal or kidney disease or dysfunction
6. History of eating disorder
7. Any diuretic
7. Taking any medication, or has any medical condition, that might interfere with the action of canagliflozin or the CGM sensor

9.4 Withdrawal

Participants are free to withdraw from the study at any time. They can do so by notifying the Principal Investigator through email or phone call. Participants can provide consent whether or not to allow use of data obtained up to that moment.

10 Schedule of Assessments and Procedures

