Objectives: Primary: To measure the effects that canagliflozin intervention has on reducing average glucose in healthy individuals. Secondary: To assess the tolerability and side effects and urinary glucose excretion following the pulsatile dosing protocol.
Methodology: 
1. Candidates will be offered participation through word of mouth and AgelessRx platform.2. Once screened and enrolled, participants will be randomized into one of two arms (A and B) and provided with all items included in the materials list below.3. Arms A & B:
a Day 0: Participants will attach a continuous glucose monitor (CGM) and follow instructions for calibration period.b Day 1 – 14: Participants will take morning blood pressure readings, and keep dietary intake journal via Lifesum.c Day 7: Participant completes Urine Collection Kit #14. Arm A:
a Day 8 - 14: Participants take 100mg Invokana (canagliflozin) with first meal daily.b Day 15: 24h after final dose, Participant completes Urine Collection Kit #2c Day 16: 48h after final dose, Participant completes Urine Collection Kit #3d Day 17: 72h after final dose, Participant completes Urine Collection Kit #45. Arm B:
a Day 8 - 14: Participants take 150mg Invokana (canagliflozin) with first meal daily, every other day for a total of 4 doses.b Day 15: 24h after final dose, Participant completes Urine Collection Kit #2c Day 16: 48h after final dose, Participant completes Urine Collection Kit #3d Day 17: 72h after final dose, Participant completes Urine Collection Kit #4
Number of subjects planned: Up to 20 healthy individuals via telehealth administration, 10 individuals in each Arm.

Diagnosis and main criteria for inclusion: Subjects will be healthy and of any sex, any ethnicity, and any age from 18-85. Participants must be approved by AgelessRx Medical Team for use of canagliflozin. They also require a CGM-compatible mobile device ([defined here](#))

Test product, dose, and mode of administration (proposed): The tablets will be from the brand Invokana and have a dosage of 100 mg or 300 mg per tablet. Investigational drugs are to be administered orally. Investigational drugs will be provided by Curexa Pharmacy, [name]

Duration of treatment: 7 days

Criteria for evaluation:

Efficacy:

- CGM data
- Urinary glucose

Safety:

- Tolerability

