6.4 Rationale and Hypothesis

Canagliflozin is a prime candidate to reduce glucose spikes and blood sugar. It has consistently acted to treat type 2 diabetes and has been shown to improve biomarkers such as fasted glucose and glucose spikes.

The current FDA-approved use of the drug is for use together with diet and exercise to treat type 2 diabetes. Canagliflozin is sometimes used in combination with insulin or other diabetes medications taken orally. It is routinely prescribed at equal or higher doses than the ones proposed in this trial.

AgelessRx Trial doses: 100 mg and 150 mg doses, taken every day and every-other day, respectively.

FDA-approved dose: Maximum recommended dose: 300 mg once daily.

Some possible side effects at the FDA-approved doses include hypoglycemia, indigestion, nausea, UTI, increased urination or thirst, hypotension, ketoacidosis, dehydration, and headache. The doses we propose have potential for some side effects, though the drug is generally well tolerated.

This trial will use a lower dose than the maximum one recommended by the FDA. We are using a maximum of 150 mg in one day vs the maximum of 300 mg each day recommended by the FDA. At this smaller dose, side effects are less common⁸. This dose has been shown to be generally safe.

Our hypothesis is three-fold:

1. Canagliflozin can be used safely and is well tolerated at doses of 100 mg per day or 150 mg every two days in healthy, non-diabetic individuals.
2. Usage of canagliflozin at these doses can effectively reduce glucose spikes (and their detrimental effects) and blood sugar levels measured by CGM in a healthy population.
3. Usage on alternate days will be effective as measured by our endpoints.

7. Objectives

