7.2 Secondary Objective

To assess the tolerability and side effects of the dosing protocol, and measure urinary glucose excretion.

8 Experimental plan

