8.1 Study Design

This study is designed to mitigate the effects of glucose with intermittent oral Canagliflozin for healthy, non-diabetic volunteers of any sex who enroll in the study. The volunteers can be within 18-85 years of age at the time of enrollment. Participants will provide informed consent via AgelessRx EMR. If eligible, prescriptions will be provided online through the AgelessRx website (www.agelessrx.com). Participants will be randomized into two arms: Arm A will take 100 mg of canagliflozin each day for a total of 7 doses, while Arm B will take 150 mg of canagliflozin every other day for a total of 4 doses. Participants in Arm B will also be provided a pill cutter to use throughout the trial on the 300mg tablet.

All participants will begin the trial on the day that they apply a continuous glucose monitor (considered Day 0) and will be asked to take daily blood pressure reading. After one week of baseline readings, both arms will start their canagliflozin dosing protocols.

Participants will be asked to complete 7 total surveys to outline side effects and tolerability, one each day starting after their canagliflozin consumption.

Participants will be asked to complete a dietary intake journal through Day 0 – Day 14. Lifesum (<https://lifesum.com/>) should be used to track Carbohydrate/Protein/Fat consumption. Participants will share their dietary intake journal twice over their participation (Day 7 & Day 14).

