10.3 Safety and efficacy evaluations

The primary endpoint, average glucose, will be assessed by examining blood glucose (mg/dL) area under curve as measured by CGM. Glucose data on days without canagliflozin treatment will serve as a control.

The secondary endpoints of safety and tolerability and urinary glucose excretion will also be assessed. Safety and tolerability will be measured by adverse event reporting, blood pressure monitoring, and by comparing treatment tolerability survey results with control tolerability results through subjective surveys. Urinary glucose excretion will be measured by at-home glucose testing strips.

11 Investigational Product

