12.3 Reporting of Adverse Events

12.3.1 Routine

The principal investigator will be notified about any adverse events. Furthermore, this information will be obtained through monitoring forms sent out to participants.

The Principal Investigator will document this information in the participant's medical record. Participants will be asked to report any serious adverse event immediately to the Principal Investigator. This can be done by email or phone (after hours phone number is available).

AEs will be documented using standard AE reporting (FDA regulations 21CFR314.80 and 21CFR213.32(s)). Both expected (already known) and unexpected AEs will be reported.

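### Section 9.4 lets a participant who withdraws from the study withhold data already collected, with no exception for safety data, so the tolerability result can lose people because of how they fared on the drug.

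*Combined protocol and SAP*

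**What the plan says.** Section 9.4 gives an open right to leave, "Participants are free to withdraw from the study at any time", and then a rule for data already in hand: "Participants can provide consent whether or not to allow use of data obtained up to that moment". It does not say when the choice is made or what happens if the person says nothing. It does not set any type of data apart, and it does not ask for the reason for withdrawal to be recorded.

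Tolerability is central to the trial. The first hypothesis in 6.4 is that "Canagliflozin can be used safely and is well tolerated at doses of 100 mg per day or 150 mg every two days". The secondary objective in 7.2 is "To assess the tolerability and side effects of the dosing protocol, and measure urinary glucose excretion". Under 10.3, "Safety and tolerability will be measured by adverse event reporting, blood pressure monitoring" and by subjective surveys. Section 8.1 adds that "Participants will be asked to complete 7 total surveys to outline side effects and tolerability", one a day from the start of dosing. The Synopsis sets the size: "Up to 20 healthy individuals via telehealth administration, 10 individuals in each Arm".

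Two other places bear on the point. Section 12.3.1 has the investigator document adverse events in the medical record and states: "Both expected (already known) and unexpected AEs will be reported". Section 12.3.2 sends serious events to the IRB within 48 hours. Neither makes this depend on consent to data use. Section 11.3.1 separately allows the drug to be adjusted or stopped for adverse events, without saying that the person leaves the study.

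Section 13 plans descriptive summaries and analysis of variance. It defines no safety population, no denominator, no treatment of withdrawn participants and no summary of withdrawals.

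**The concern.** A rate of side effects can be interpreted only if the people counted were not chosen by their outcome. Under 9.4, inclusion of a withdrawn person's record depends on a choice that, read naturally, is made after taking the drug. If the people who withdraw and refuse are mainly those who felt unwell, the remaining participants look more tolerant than the group that was dosed. With 10 people in an arm, one or two such losses can remove the signal altogether. The loss could also differ between the daily and alternate-day arms.

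Surveys and blood pressure are the most exposed. Non-serious adverse events may be exposed too, depending on how 9.4 and 12.3 are read together. Baseline and on-drug CGM days for the primary endpoint would also go.

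**Working it through.** The plan states no withdrawal rate, adverse event rate, power or tolerability threshold, so it has no figure to reproduce. The check is whether the rule can move the result, and by how much under stated assumptions.

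**Inputs.** From the Synopsis: N = 10 per arm, 20 in all. Assumed: x people have a tolerability event, and k of those x withdraw from the study and refuse use of their data.

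**Formula.** The rate among all dosed is x/N. The rate reported after the loss is (x − k)/(N − k). The fall is x/N − (x − k)/(N − k) = k(N − x)/[N(N − k)], which is above zero whenever k ≥ 1 and x < N.

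**Results, with exact (Clopper-Pearson) 95% intervals.**

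| All dosed | Withheld | Reported |
|---|---|---|
| 1/10 = 10% (0.3% to 44.5%) | 1 | 0/9 = 0% (0% to 33.6%) |
| 2/10 = 20% (2.5% to 55.6%) | 2 | 0/8 = 0% (0% to 36.9%) |
| 3/20 = 15% (3.2% to 37.9%) | 2 | 1/18 = 5.6% (0.1% to 27.3%) |

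For zero events in n people the upper limit is 1 − 0.025^(1/n). With n = 8 this gives 36.9%.

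**Range.** In one arm, a single withheld person with an event lowers the rate by 4.4 points (from 6/10) to 10.0 points (from 1/10). Two lower it by 10.0 points (from 6/10) to 20.0 points (from 2/10). With all 20 pooled, one lowers it by 3.7 points (from 6/20) to 5.0 points (from 1/20).

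**Chance of any such loss.** Let p be the probability of withdrawing for side effects and w the share of those people who refuse data use, both assumed. The chance of at least one among 20 is 1 − (1 − pw)^20. With w = 0.5:

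- p = 0.05: 1 − 0.975^20 = 40%.
- p = 0.20: 1 − 0.90^20 = 88%.

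The rate of such withdrawals then seen is about p(1 − w)/(1 − pw). That is 0.025/0.975 = 2.6% in place of 5%, and 0.10/0.90 = 11.1% in place of 20%.

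**Direction.** It depends on who leaves. If one person without an event withdraws and refuses, 2/10 becomes 2/9 = 22.2%, which makes the drug look worse.

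**9.4 against 12.3.** Section 9.4 governs use of study data. Section 12.3 governs documenting and reporting adverse events. Both can be obeyed at once: an event can be recorded and reported, and still be left out of the trial's tolerability result. The documents do not say whether it would be.

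**The case against.** The case on the other side has several parts.

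- **Timing and default.** Section 9.4 does not state when the choice is made. Section 14.2 describes yes/no answers to individual consent lines before signing, so this could be a pre-enrolment item. In that case refusal could not depend on side effects, though withdrawal still could. The consent text in Appendix A is not in the material available and may settle the matter. This stands as an uncertainty. The reference to data up to the moment of withdrawal still fits a choice made then better than one made in advance.
- **Conflict with 12.3.1.** A reader might infer that the two sections contradict each other. They do not: 12.3.1 says that expected and unexpected events will be reported, and it does not promise that every event enters the analysis. What remains is an unreconciled boundary. Section 12.3 is a real, partial safeguard, strongest for serious events.
- **Stopping the drug.** A reader might also infer that anyone who stops because of side effects disappears from the result. That is not supported. Section 11.3.1 covers stopping the drug, and only a person who leaves the study and also refuses data use is lost.
- **Direction and size.** Nothing in the documents shows that poor tolerability will be the main reason to leave. There is also a drug-free baseline week, a sensor, a diet journal, daily blood pressure and four urine kits, and withdrawals due to that burden need not flatter the drug. The counts above are assumptions, and the intervals overlap widely. This stands.
- **Autonomy.** Letting people withhold data is a defensible choice. But the Declaration of Helsinki text in Appendix E protects the right to withdraw from participation (paragraph 26), which the fix preserves. It also holds researchers responsible for full and accurate reporting (paragraph 36).

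**Conclusion.** The point holds as a risk that the plan permits. It is not a bias that the documents show will occur. Section 9.4 allows data already collected to be withheld, exempts no safety data, and is not offset by any denominator or withdrawal rule in section 13. If people who withdraw from the study because of side effects also refuse use of their data, the tolerability result moves in the favourable direction. Illustrated at two people in one arm, 20% becomes 0%.

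This rests on three assumptions: that the choice is made at withdrawal, that those who refuse tolerated the drug worse than those who stay, and that the illustrative counts are plausible. The documents support the first as the natural reading and give no figures for the other two. The true size cannot be computed from them.

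**What to change.** Amend 9.4, with a matching line in the consent given before enrolment:

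- Data collected up to withdrawal are kept and analysed in the assigned arm. At minimum this covers adverse event, survey, blood-pressure and dosing data. The participant may refuse any further collection and may still leave at any time.
- State in 9.4 or 12.3 that adverse events documented before withdrawal count in the tolerability result.
- In section 13, report by arm the number dosed and the number withdrawn, with the reason where given.
- If any option to withhold data is kept, state when the choice is made and what applies if none is expressed. Report the number withheld by arm, and add a worst-case sensitivity analysis that counts those people as not tolerating the drug. In the two-person illustration this restores 0/8 to 2/10.

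The cost is a sentence in 9.4, a line in the consent, short additions to the safety reporting and statistical sections, and submission to the IRB. The real downside is that participants lose the option to erase past data.

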10.0 Patient Recruitment

Candidates will be offered the opportunity to participate in this interventional trial after approval of canagliflozin through the AgelessRx platform and expressing interest via screening questionnaire.

10.1 Screening

Candidates will be offered the opportunity to participate in this trial after approval of canagliflozin prescription through the AgelessRx platform. Patients must proceed through medical intake, consent to participate, consultation with the AgelessRx medical team (synchronously or asynchronously, depending on the regulations of the state in which the candidate resides), and approval before receiving their treatment. Medical intake will be reviewed by the AgelessRx medical team and consent responses will be reviewed by the research coordinator. Once the candidate has been approved for their canagliflozin prescription and the patient has expressed interest and consented to participation, the AgelessRx research coordinator will contact the candidate for additional instruction. The medical intake and consent built into the patient process will include inclusion/exclusion screening criteria and will serve as a screening tool for medical and research personnel. The consent language built into the patient intake workflow can be found in Appendix A. Identity validation will occur prior to product intake submission and will be verified following consent completion, as a photo of self and I.D. are required before the patient may proceed. Informed consent will be captured via free text name entry within the consent questionnaire.

10.2 Enrollment

Participants will be enrolled in the study for a total of two weeks. After the two weeks, participants will be free to use the trial drug off-label as they choose.

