11.3 Dosing and Administration

11.3.1 Dose Escalation, Dose Adjustments, Stopping Rules

Participants will receive 100 mg tablets or 300 mg tablets, broken in half. There will be no dose escalation in this study. Dose adjustments or discontinuation of the drug can be made based on adverse events in a participant, which will be discussed in a phone call between the participant and Research Coordinator.

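### Section 10.2 frees participants to take canagliflozin after two weeks, before the three post-dose urine kits on Days 15–17 are collected

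*Combined protocol and SAP*

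**What the plan says.** Section 10.2 sets the length of participation: "Participants will be enrolled in the study for a total of two weeks". It continues: "After the two weeks, participants will be free to use the trial drug off-label as they choose". This is the only supplied text on drug use after the two weeks.

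The synopsis (Methodology) has both arms dosing over Days 8–14. For Arm A: "Participants take 100mg Invokana (canagliflozin) with first meal daily". Arm B takes 150 mg with the first meal on alternate days, four doses in all. Both arms then have three urine kits timed from the last dose, on Days 15, 16 and 17, ending with: "Day 17: 72h after final dose, Participant completes Urine Collection Kit #4". The synopsis also gives "Duration of treatment: 7 days".

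Section 10.3 names urinary glucose excretion as a secondary endpoint. Apart from the three kits above, the only scheduled urine collection is the baseline Kit #1 on Day 7.

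Other scheduled records stop at about Day 14. Blood pressure (synopsis) and the diet journal (synopsis and Section 8.1) end that day. On tolerability, Section 8.1 says: "Participants will be asked to complete 7 total surveys to outline side effects and tolerability, one each day starting after their canagliflozin consumption".

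**The concern.** The kit labels are meaningful only if nothing is taken between the Day 14 dose and Kit #4. Section 10.2 permits the opposite over exactly those days.

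Redosing is plausible. Interest in taking the drug is an inclusion criterion (Section 9.2), and candidates enter the trial "after approval of canagliflozin prescription through the AgelessRx platform".

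It could also go unnoticed, since no supplied text schedules a record of dosing on Days 15–17. Doses go with the first meal, so 24 h after a dose is about the time of the next first meal. The schedule does not fix whether a kit comes before or after a new dose that day.

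Canagliflozin acts by raising urinary glucose (Sections 6.2 and 11.1). A sample taken after a new dose would therefore tend to read high and be attributed to the Day 14 dose. That error would favour the third hypothesis in Section 6.4, that alternate-day use is effective.

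A smaller point concerns safety. Section 12.3.2 ties expedited SAE reporting to active participation, although it also refers to the study remaining open at the IRB. If enrolment ends at two weeks, coverage on the three kit days is unclear.

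**Working it through.** **Calendar.** Inputs are from the synopsis and Sections 8.1 and 10.2.

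- Arm A: daily on Days 8–14 gives 7 doses, the last on Day 14. This matches the stated 7.
- Arm B: Days 8, 10, 12 and 14 give 4 doses, the last on Day 14. This matches the stated 4.
- Kits: (15 − 14) × 24 = 24 h, (16 − 14) × 24 = 48 h, (17 − 14) × 24 = 72 h. The labels are right in both arms if no further dose is taken.
- Two weeks end on Day 14 counting from Day 1, or on Day 13 counting from Day 0. On either count all three kits fall after enrolment.
- Samples: 20 × 3 = 60 post-baseline, out of 20 × 4 = 80 in total.

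**Effect of redosing on the labels.** There are 2³ − 1 = 7 patterns with at least one new dose on Days 15, 16 and 17 (1 = dose). Entries are nominal hours since the last dose at Kits #2/#3/#4, with 0 meaning a dose earlier the same day. The labels are 24/48/72.

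| Days 15, 16, 17 | Kit before that day's dose | False labels | Kit after that day's dose | False labels |
|---|---|---|---|---|
| 001 | 24/48/72 | 0 | 24/48/0 | 1 |
| 010 | 24/48/24 | 1 | 24/0/24 | 2 |
| 011 | 24/48/24 | 1 | 24/0/0 | 2 |
| 100 | 24/24/48 | 2 | 0/24/48 | 3 |
| 101 | 24/24/48 | 2 | 0/24/0 | 3 |
| 110 | 24/24/24 | 2 | 0/0/24 | 3 |
| 111 | 24/24/24 | 2 | 0/0/0 | 3 |

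The patterns are counted, not weighted by likelihood. The upper limits, if all 20 redose on Day 15, are 20 × 2 = 40 mislabelled samples (kit before dose) or 20 × 3 = 60 (kit after dose).

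**Arms.** Participants who choose the same days have the same number of false labels in either arm. If each arm simply continued its assigned schedule, Arm A would be 111 and Arm B 010. That gives 2 v 1 false labels per participant (kit before dose) or 3 v 2 (kit after dose).

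**Effect on an arm mean.** With 10 per arm, if k participants redose on Day 15, the 48 h mean shifts by (k/10) × (reading after the new dose − true 48 h reading). The plan gives no redosing rate, so k is an assumption: k = 0, 1, 3 or 5 gives a shift of 0, 10, 30 or 50% of that gap. The gap itself is not given either.

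**Supply.** Section 11.3.1 says: "Participants will receive 100 mg tablets or 300 mg tablets, broken in half". Planned doses need 7 tablets of 100 mg in Arm A, and 4 halves = 2 tablets of 300 mg in Arm B. The number dispensed is not stated.

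**The case against.** The strongest reply is that the kit schedule already implies a washout. If someone redosed on Day 15, Day 14 would no longer be the final dose, and the treatment duration is stated as 7 days. On this view Section 10.2 is a loose two weeks that overlooked Days 15–17. That may be how it arose. But those statements define trial dosing; they do not prohibit the own use that Section 10.2 expressly allows.

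Second, the consent text (Appendix A), the design figure and the coordinator's instructions are not in the supplied text, and any of them might tell participants to wait. This stands as a limit: one cannot say that no abstinence instruction exists anywhere. If one does, Section 10.2 contradicts it and still needs changing.

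Third, the size is not established. The count of 60 is of samples scheduled, not samples affected. If kits always precede that day's dose, the 24 h label is never false. Leftover tablets are not shown, and the redosing rates above are assumed. All of this stands.

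Fourth, only a secondary endpoint is touched, and Section 13 specifies no urinary glucose analysis or between-arm comparison. This also stands, and it limits the severity.

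Fifth, the SAE point is weak: Section 12.3.1 asks for immediate reporting of any SAE with no Day 14 cut-off, and a person completing kits may well count as participating. It supports no more than a request for clarity.

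**Conclusion.** The concern holds, and the plan should be changed. Followed as written, Section 10.2 allows dosing that could contaminate every post-baseline urine sample (up to 60 of 80) with no scheduled record to reveal it. The likely direction is false persistence of urinary glucose excretion.

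The conclusion rests on the calendar and on the absence of an abstinence rule or dosing record in the supplied text. It does not depend on an assumed redosing rate. The size of the bias cannot be stated. A bias that differs between arms is possible but not established, and no effect on the primary CGM endpoint is shown.

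**What to change.** Reword Section 10.2 to say three things: participation, including AE and SAE capture, runs until Kit #4 is complete (Day 17); no canagliflozin is taken between the Day 14 dose and completion of Kit #4; and off-label use may begin only after that. Make sure the consent text and coordinator instructions agree.

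Add one line to each kit form for the date, time and amount of the last dose. Analyse any kit taken after a new dose by actual time since that dose. Leave such kits out of the nominal 24/48/72 h summary only as a sensitivity analysis.

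The cost is a wording change, one line per form, and a wait of up to three days that the kit schedule already presupposes. The analysis has two drawbacks. Using actual times gives uneven numbers at 24, 48 and 72 h. Dropping kits selects on participant choice, since redosers may differ in tolerance or response, and it loses precision.

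For the loss of precision, the 95% CI half-width for an arm mean, in SD units, is t(0.975, n − 1)/√n. This is 0.715 at n = 10, 0.769 at 9, 0.836 at 8 and 0.925 at 7. With the same SD, dropping 1, 2 or 3 of 10 kits widens the interval by about 7%, 17% or 29%. The abstinence rule is there to keep both drawbacks small.
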